2.5.2 PHARMACOKINETICS AND PHARMACODYNAMICS DATA FOR ONCE-WEEKLY DOSING

Pharmacokinetics (PK) and pharmacodynamics (PDn) results from CHAMPION 1 are supportive of the proposal to study the once-weekly 70 mg/m² regimen as an effective alternative regimen for carfilzomib.

Preliminary PK results from CHAMPION 1 indicated that a once-weekly 30-minute infusion of carfilzomib had a mean terminal half-life similar to the half-life of ≤ 1 hour following the approved twice-weekly dosing regimen (20/27 mg/m² over 2 to 10 minutes). In addition, the data showed a dose-proportional increase in the mean C_{max} and area under the curve (AUC) from 20 to 88 mg/m², as indicated by the similar dose normalized values for C_{max} and AUC (refer to [Table 1](#)). The AUC following a 70 mg/m² dose was 1045 ng·h/mL, which is higher than the total weekly AUC following the twice-weekly of 27 mg/m² dose (758 ng·h/mL, refer to [Table 2](#)). The mean C_{max} following the 70 mg/m² dose administered as a 30-minute infusion is 2640 ng/mL, which is lower than the mean C_{max} of 4232 ng/mL in Study PX-171-003 – Part 2 (A1), following the IV infusion of 27 mg/m² over 2 to 10 minutes ([Carfilzomib IB](#)).

Table 1 Summary of Pharmacokinetic Parameters from CHAMPION 1

Dose (mg/m ²)	n	t _{1/2} (%CV)	C _{max} (%CV)	C _{max} /Dose (ng/mL)/mg/m ²	AUC _{0-last} (%CV)	AUC/Dose (h·ng/mL)/mg/m ²
20	11	0.77 hr (37.4%)	703 ng/mL (16.0%)	35.0	283 ng·h/mL (17.6%)	14.2
70	5	0.91 hr (24.3%)	2640 ng/mL (24.9%)	37.7	1045 ng·h/mL (22.1%)	14.9
88	5	0.84 hr (11.3%)	3172 ng/mL (24.9%)	36.0	1247 ng·h/mL (31.3%)	14.2

AUC_{0-last} = AUC from time 0 to last time measurable concentration, CV = coefficient of variation, t_{1/2} = terminal half-life, C_{max} = maximum plasma concentration, AUC = area under the curve.

Table 2 Pharmacokinetic Parameters Comparison of CHAMPION 1 and PX-171-003 – Part 2 (A1)

Study	Cycle/Dose/Days	Infusion Duration	Total dose/week (mg/m ²)	Total AUC per week (ng·hr/mL)	Maximal concentration (ng/mL)
PX-171-003 – Part 2 (A1)	Cycle 1: 20 mg/m ² Days 1, 2, 8, 9, 15, and 16	2–10 minutes	40	566 ^a	3060
	Cycle 2: 27 mg/m ² Days 1, 2, 8, 9, 15, and 16	2–10 minutes	54	758 ^a	4232
2012-002 (CHAMPION 1)	Cycle 1 Day 1: 20 mg/m ² Cycle 1 Days 8 and 15: 70 mg/m ²	30 minutes	70	1045 ^b	2640
	Cycle 2: 70 mg/m ² Days 1, 8, and 15	30 minutes			

AUC = area under the curve.

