^a AUC following a single 20 and 27 mg/m² dose (2–10 minutes infusion) is 283 and 379 ng·hr/mL, respectively. Total AUC per week is calculated by multiplying the single dose AUC by 2 (e.g., 379 × 2 = 758 ng·h/mL).

^b Represents total AUC per week starting on Day 8.

[figure not shown]
An exploratory exposure response analysis indicates a statistically significant relationship between the carfilzomib average AUC during Cycle 1 and response rates (ORR and CBR) with higher AUC exposures associated with improved responses in subjects with multiple myeloma (TR-1092-171). No statistically significant relationships between C_{max} and efficacy or safety endpoints were found.

Preliminary PDn data from CHAMPION 1 revealed that in blood and peripheral blood mononuclear cells (PBMCs) the 70 mg/m² dose level resulted in a greater depth of proteasome inhibition, at 1-hour post dose, compared to 1 hour after the Cycle 2 Day 1 dose in a twice-weekly schedule of 27 mg/m² and 56 mg/m² (as observed in the Phase 1b/2 PX-171-007 study). Chymotrypsin-like subunits (Beta 5 and latent membrane protein 7 [LMP7]) were inhibited most strongly, followed by trypsin-like (Beta 2 and multicatalytic endopeptidase complex-like 1 [MECL-1]), and caspase-like (Beta 1 and latent membrane protein 2 [LMP2]) subunits, respectively (refer to [Figure 1](#)).

Together, PK and PDn results from CHAMPION 1 support the investigation of once-weekly 70 mg/m² regimen as a potentially effective alternative regimen for

carfilzomib. The PK results from this study indicate that the total AUC per cycle delivered by the 70 mg/m² dose is expected to be higher compared to those of the 20/27 mg/m² regimen, consistent with the high ORR observed in the study (Berenson 2014) and exploratory exposure response analysis for carfilzomib (TR-1092-171). Pharmacodynamics data are consistent with a greater depth of proteasome inhibition with 70 mg/m² compared to those at 27 mg/m² and 56 mg/m² (as observed in the Phase 1b/2 PX-171-007 study).

Figure 1 Proteasome Percent Activity in Peripheral Blood Mononuclear Cells

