10.7.1 Exposure-Response (E-R) Analysis

PK data collected from individuals who consent to the sparse PK sampling or PK/PDn sub-study will be used to explore the E-R relationship for efficacy and safety endpoints. The data from this study will be used to update a previously developed E-R model (Amgen Pharmacometrics Report: 121604) and will be described in a separate report.

In brief, each exposure metric will be calculated using the individual subject's parameters from the population PK model (see Section 10.7 Analysis plan for sparse PK data) and dosing history. The exposure metrics will be computed from the estimated Cmax and AUC and combined with the response/adverse event data to examine the E-R relationships for efficacy and safety endpoints. A pooled analysis of data from this study and other carfilzomib clinical studies will be conducted. In addition, an E-R analysis based on this study alone may also be conducted.

Categorical responses will be tabulated by count and proportion by study. In the analysis, a quantitative assessment of the effect of each of the exposure metrics will be

Statistical Analysis Plan: 20140355

Date: 09 Jun 2017 Page 36

performed either using logistic regression for binary endpoints or log-rank test by exposure quartile for time-to-event endpoints. Endpoints exhibiting a statistically significant relationship to carfilzomib exposure will be further evaluated with multiple logistic or Cox proportional hazards models (for time-to-event endpoints) to assess the effects of covariates in conjunction with carfilzomib exposure on efficacy and safety responses. Additional multiple logistic regression analysis will not be performed on the endpoints that showed inverse relationship.

Efficacy endpoints

The efficacy endpoints will include Progression-free survival (PFS), ORR and CBR.

Safety endpoints

Safety endpoints will include the subject incidence of any grade adverse events leading to study drug discontinuation, any Grade 3 or higher adverse events, serious adverse events, TEAEs with a fatal outcome, and cardiac, hepatic, and renal adverse events. Additional endpoints of interests may be included in the analysis.

Covariates of interest

Endpoints exhibiting a statistically significant relationship to carfilzomib exposure will be further evaluated with multiple logistic models. The key covariates tested in the multiple logistic regression analysis may include the following:

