bortezomib refractory in any prior regimen (yes/no), number of prior regimens, Eastern Cooperative Oncology Group (ECOG) performance status, sex, age, race, baseline CrCL, baseline hemoglobin (g/L), baseline serum beta-2 microglobulin (mg/L), and baseline platelet count (<150, ≥150 [10⁹/L]). Additional covariates of interests may be included in the analysis.

11. Changes From Protocol-specified Analyses

In the protocol, it specifies that logistic regression model will be used for ORR analysis. However, since Cochran-Mantel -Haenszel test is more widely used in analysis of binary endpoints to support regulatory filings, Cochran-Mantel-Haenszel test is specified to be used for ORR analysis in the SAP. The CMH test statistic and the score test statistic of the conditional logistic regression are approximately identical (Day N.E.& Byar D.P., 1979), so this analysis method change will not affect the conclusion of ORR analysis.

Statistical Analysis Plan: 20140355

Date: 09 Jun 2017 Page 37

12. Literature Citations / References

Clopper CJ and Pearson ES. The use of confidence or fiducial limits illustrated in the case of the binomial, Biometrika. 1934; 26(4):404-413.

Collett D. Modelling Survival Data in Medical Research. 2nd edition. London, UK: Chapman & Hall/CRC; 2003.

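### The exposure-response screen in SAP 10.7.1 pools two regimens without adjustment and fixes no exposure window, so a regimen or study difference can be reported as an AUC effect

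*SAP*

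**What the plan says.** SAP 10.7.1 plans an exploratory analysis of PFS, ORR, CBR and several adverse-event incidences against metrics computed from each subject's estimated Cmax and AUC and dosing history. Four features matter here.

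- **Pooling.** "A pooled analysis of data from this study and other carfilzomib clinical studies will be conducted". An analysis of this study alone is optional.
- **First stage.** The effect of each metric is assessed by a test "performed either using logistic regression for binary endpoints or log-rank test by exposure quartile for time-to-event endpoints". No stratification or covariate is stated.
- **Second stage.** Only endpoints with a significant relationship go on to multiple logistic or Cox models. Endpoints with an inverse relationship get no additional multiple logistic regression.
- **Covariates.** The list begins "bortezomib refractory in any prior regimen (yes/no), number of prior regimens, Eastern Cooperative Oncology Group (ECOG) performance status" and continues with sex, age, race and baseline laboratory values. Regimen, dose, infusion time and study are not named. The list is permissive and allows additions.

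The window over which exposure is summarised is not defined.

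On exposure by regimen, protocol 2.5.2 says: "The AUC following a 70 mg/m² dose was 1045 ng·h/mL, which is higher than the total weekly AUC" of the twice-weekly 27 mg/m² regimen, 758 ng·h/mL. The same section describes an earlier exploratory analysis that related average AUC during Cycle 1 to ORR and CBR.

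**The concern.** The arms differ in dose per infusion, number of infusions and infusion time, as well as in AUC. When subjects from both arms are ranked together by AUC, the upper quartiles fill with once-weekly subjects. Any difference in outcome between the arms, whatever its cause, then also appears between AUC quartiles. Adding other studies brings study differences in by the same route.

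A covariate model at the second stage does not fully repair this. The unadjusted result has already chosen which endpoints get a model, and a binary endpoint with an inverse relationship gets no multiple logistic model.

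The open window raises a separate problem. The first week of treatment is given at the 20 mg/m² step-up dose, so exposure averaged up to progression rises with time on treatment. In the PFS analysis, a metric of that kind depends on the outcome it is meant to explain.

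At stake is how a trial comparing dose and schedule gets interpreted: a regimen difference could be reported as a concentration effect.

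**Working it through.** **Plan's own figures.** Weekly AUC for the twice-weekly regimen (protocol Table 2, note a): 379 × 2 = 758, and 283 × 2 = 566. Both reproduce.

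**AUC ratio by window** (single-dose AUCs from protocol Tables 1 and 2; schedule from protocol 2.5):

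| Window | Once weekly | Twice weekly | Ratio |
|---|---|---|---|
| Cycle 1 | 283 + 2 × 1045 = 2373 | 2 × 283 + 4 × 379 = 2082 | 1.14 |
| Cycle 2 onward | 3 × 1045 = 3135 | 6 × 379 = 2274 | 1.38 |

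**Regimen artefact.** Simulated trials had a regimen effect on PFS but no exposure effect within either arm.

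- Exposure: log-normal around the table means. CV was 22.1% in the once-weekly arm (protocol Table 1, n = 5) and 22% to 40%, assumed, in the other arm.
- PFS: exponential, medians 8.2 and 6 months (hazard ratio 6/8.2 = 0.73). These medians appear only in superseded text in the amendment log and serve here as an assumption.
- Accrual 15 months, cutoff 25 months, 500 trials per setting. The Monte Carlo standard error is about √(0.28 × 0.72/500) = 2 points at 28%, and 1 point at 5%.
- Test: log-rank over pooled exposure quartiles (3 df), 5% level.

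| Metric | Subjects per arm | Unadjusted, p < 0.05 |
|---|---|---|
| Weekly AUC | 115 | 16–17% |
| Weekly AUC | 230 | 27–29% |
| Cycle 1 AUC | 230 | 9% |

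With regimen as a stratum, rejection was 4% to 7% in these settings. A rerun with censoring uniform on 10 to 25 months gave 18% (230 subjects) and 29% (460) for weekly AUC, and about 8% to 9% for Cycle 1 AUC. For weekly AUC with 230 per arm, the once-weekly arm filled 75% to 89% of the top quartile, and higher AUC looked better in 96% to 97% of trials.

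For binary endpoints, with an assumed ORR of 60% against 45%, unadjusted logistic regression on log AUC rejected in 39% to 52% of trials at 230 per arm and 24% at 115 per arm. With regimen in the model it rejected in 4% to 6%. With no regimen effect, the unadjusted tests on weekly AUC rejected at about 5%.

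**Averaging window.** The mean once-weekly dose per cycle after k cycles is (160 + 210(k − 1))/k: 160 mg/m² at k = 1 and 1630/8 = 203.75 at k = 8, which is 27% higher with no dose change. The twice-weekly equivalent is 148, then (148 + 7 × 162)/8 = 160.25, which is 8% higher.

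With neither a regimen nor an exposure effect (both medians 7 months), the quartile log-rank on AUC averaged over treatment rejected in 22% to 44% of trials with 230 to 460 subjects, nearly always in the favourable direction. With a Cycle 1 window it rejected in 4% to 6%. With medians 8.2 and 6 months, stratifying by regimen and forming quartiles within regimen still left 27% to 52% for the averaged metric.

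**Cmax.** Protocol 2.5.2 gives a once-weekly mean of "2640 ng/mL, which is lower than the mean C_{max} of 4232 ng/mL in Study" PX-171-003, "following the IV infusion of 27 mg/m² over 2 to 10 minutes". In this trial the twice-weekly arm is infused over about 10 minutes and the once-weekly arm over about 30 (protocol 9.2.1.1). Infusion rates are 27/10 = 2.70 and 70/30 = 2.33 mg/m²/min, ratio 1.16. Under linear kinetics the twice-weekly Cmax is at most 1.16 × 2640, about 3055 ng/mL. At that cap the pooled quartile log-rank rejected in 7% of trials. At a twice-weekly Cmax of 2274 (379 divided by 1/6 h), the sign was mostly reversed.

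**The case against.** Several counter-arguments have weight.

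- **Non-prespecification, not exclusion.** The covariate list is permissive and open-ended, and the section defers to a separate modelling report that is not among the documents. A reader might infer that the plan rules regimen out; it does not. But an open list for the second stage does not reach the unadjusted first stage, or a binary endpoint dropped as inverse.
- **AUC may mediate the regimen effect.** Higher AUC with better response is the trial's own rationale. A regimen term removes the randomised contrast and leaves non-randomised variation in exposure within arms. This stands, and it is why both results should be shown.
- **The mandatory analysis includes other studies.** The simulations contain only this trial's two arms. Other doses would spread the quartiles, so the quartile shares do not describe the full pooled analysis. This stands; study differences then become a further source of confounding.
- **Averaging to the event is not stated.** Dose reductions could also cancel the rise. Using the decrements in protocol Table 3 from Cycle 2, the eight-cycle average is (160 + 7 × 168)/8 = 167 after one and (160 + 7 × 135)/8 = 138 after two, against 160 in Cycle 1. The bias is therefore conditional, but the SAP leaves that choice open.

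A reader might also infer from 2640 against 4232 ng/mL that Cmax must show an inverse artefact. The documents do not support that: the higher figure comes from another study with infusions as short as 2 minutes, and at this trial's infusion times the ranking may be slight or reversed.

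**Conclusion.** The point holds for AUC, and more generally for an unadjusted pooled screen. As written, SAP 10.7.1 can report a regimen or study difference as an AUC effect, and it uses that result to choose which endpoints are modelled.

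For the PFS quartile test in this trial alone, rejection without any within-arm exposure effect is roughly 15% to 30% on weekly AUC and about 8% to 9% on Cycle 1 AUC, against a nominal 5%. These sizes rest on the superseded medians, CVs partly assumed and otherwise from five subjects, and an assumed share of subjects consenting to PK sampling (half or all). The sign follows whichever arm does better. Most simulated trials show no significant AUC signal by log-rank, so the artefact is a material risk and not a certainty.

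The time-on-treatment bias arises only if exposure is averaged over treatment. Regimen adjustment does not remove it, and dose reductions could offset it. The direction of any Cmax artefact is not established.

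The analysis is exploratory; the tests of PFS, ORR and OS are unaffected.

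**What to change.** In SAP 10.7.1:

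1. Stratify the quartile log-rank by regimen, and by study when data are pooled.
2. Include regimen and study in the first-stage logistic models and in the later logistic and Cox models.
3. Apply the same adjustment to endpoints with an inverse relationship.
4. Report the adjusted result beside the unadjusted pooled one.
5. Fix the exposure window at Cycle 1, as in the earlier analysis described in protocol 2.5.2, or use time-varying exposure for PFS.

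The cost is SAP wording and a few more model runs. The range of exposure within a regimen is narrower, so a true effect is estimated less precisely. Adjustment also removes any part of the regimen effect that acts through AUC; showing both results lets the reader see that part.

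### Significant inverse exposure-response results for binary endpoints are excluded from the covariate-adjusted logistic models

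*SAP*

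**What the plan says.** SAP Section 10.7.1 describes two steps.

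- Step 1 relates each exposure metric to each endpoint with no covariates named. It is "performed either using logistic regression for binary endpoints or log-rank test by exposure quartile for time-to-event endpoints".
- Step 2 is gated on significance: "Endpoints exhibiting a statistically significant relationship to carfilzomib exposure will be further evaluated with multiple logistic or Cox proportional hazards models (for time-to-event endpoints"). Its purpose is "to assess the effects of covariates in conjunction with carfilzomib exposure on efficacy and safety responses".

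The next sentence is the exception at issue: "Additional multiple logistic regression analysis will not be performed on the endpoints that showed inverse relationship". The section gives no reason for it, does not define inverse, and names no substitute sensitivity analysis. The later paragraph on covariates of interest repeats the significance gate without the exception, but does not withdraw it.

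On endpoints, "The efficacy endpoints will include Progression-free survival (PFS), ORR and CBR". On safety, "Safety endpoints will include the subject incidence of any grade adverse events leading to study drug discontinuation, any Grade 3 or higher adverse events", followed by serious AEs, fatal TEAEs, and cardiac, hepatic and renal AEs. The candidate covariates are all baseline characteristics: bortezomib-refractory status, number of prior regimens, ECOG, sex, age, race, creatinine clearance, hemoglobin, beta-2 microglobulin and platelet count.

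Exposure metrics come from individual population-PK parameters together with dosing history. The analysis pooled with other carfilzomib studies will be done; one on this study alone is optional.

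**The concern.** Whether an endpoint is adjusted depends on the sign of its unadjusted estimate. A significant association in the expected direction is checked against patient characteristics. A significant association in the opposite direction is not, although an unexpected sign is a good reason to look for confounding.

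There are two plausible routes to a confounded inverse result here. First, Protocol Section 9.3 (Tables 4 and 5) requires carfilzomib to be withheld or reduced for several toxicities, and dosing history enters the exposure metric. Frailer subjects could therefore show lower exposure and more adverse events. Second, differences between pooled studies in population and dose are not protected by this trial's randomization.

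Exposure-response output also carries some weight in this programme: Protocol Section 2.5.2 cites an earlier exploratory analysis of this kind in support of the once-weekly 70 mg/m² regimen. At stake is the even-handedness of the exposure-response report, mainly for safety.

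**Working it through.** **1. Which endpoints the exception reaches.** There are 3 efficacy endpoints (PFS, ORR, CBR) and 7 safety incidences (discontinuation due to AE, grade 3 or higher, serious, fatal, cardiac, hepatic, renal): 3 + 7 = 10. PFS is time-to-event and its adjusted model is Cox, which the sentence does not name. The other 10 − 1 = 9 are binary and fall under the exception if the result is inverse.

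**2. What each outcome of step 1 leads to for a binary endpoint.**

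| Step 1 result | Covariate-adjusted model? |
|---|---|
| Not significant, either direction | No (significance gate) |
| Significant, expected direction | Yes |
| Significant, inverse | No (direction exception) |

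Only the last row depends on sign. For PFS the status is unclear: Cox is not barred, but the covariates paragraph speaks of multiple logistic models for all endpoints, and a log-rank comparison of quartiles has no sign until one is defined.

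**3. Size.** The section gives no sample size, alpha or effect size, so there is no plan figure to reproduce. What follows is illustration on assumed inputs: n = 400, two-sided p < 0.05 as the gate, and one baseline confounder with variance 1 that lowers exposure (correlation −ρ) and raises the log-odds of an event by γ per unit. With no true exposure effect, the unadjusted log odds ratio (OR) per SD of exposure is roughly −ργ. For example, ρ = 0.4 and γ = 0.7 give exp(−0.28) = 0.76, against 0.77 simulated.

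Binary confounder, 400 data sets per row, true OR 1.00:

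| ρ | γ | Unadjusted OR | Significantly inverse | Adjusted OR, all data sets | Adjusted OR, significantly inverse data sets only |
|---|---|---|---|---|---|
| 0 | 0 | 1.00 | 3% | 1.00 | 0.79 |
| 0.2 | 0.3 | 0.95 | 9% | 1.01 | 0.83 |
| 0.3 | 0.5 | 0.87 | 25% | 1.01 | 0.89 |
| 0.4 | 0.8 | 0.73 | 85% | 1.00 | 0.97 |
| 0.5 | 1.0 | 0.62 | 99.5% | 1.00 | 1.00 |

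Normal confounder, 50% event rate, 1000 data sets per setting, true OR 1.00:

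- ρ = 0.4, γ = 0.7: OR 0.77, significantly inverse in about 72%
- ρ = 0.2, γ = 0.7: OR 0.88, 25%
- ρ = 0.4, γ = 0.3: OR 0.89, 20%
- ρ = 0.2, γ = 0.3: OR 0.94, 8%
- ρ = 0.4, γ = 0.7 with an assumed 6% event rate, as for a rare outcome: below 30%

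**4. Masked harm.** In the binary-confounder model with a true harmful OR of exp(0.2) = 1.22, the two strongest settings give unadjusted ORs of 0.88 and 0.74, significantly inverse in 21% and 85% of data sets. Adjustment returns about 1.22 on average.

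**5. What the simulation cannot show.** The adjusted average of 1.00 is built in, because the only confounder is perfectly measured and entered in the model. The last column of the table also shows that adjusting only what passes a significance gate leaves some selection bias when confounding is weak.

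**The case against.** The strongest reply is that little depends on this. The exposure-response work is exploratory, is not among the listed objectives or endpoints, and is reported separately. Protocol Section 13.3.4 says only that such analyses may be performed. Comparative safety will be read from the by-arm tables of a randomized trial (SAP Section 10.6.1). All of that stands and keeps the point minor.

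The method paragraph is also a summary that builds on an earlier model report. Inverse may be defined or justified in a document not available here. That is possible, but the SAP sentence is categorical and nothing in the SAP or protocol qualifies it.

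A third reply is that baseline covariates would not repair the most likely distortion. If doses are held or stopped after an event, exposure falls because of the event, and no baseline variable removes that. An adjusted inverse result might even look more credible than it is. This is correct, and it limits what the fix can claim. How much it matters depends on the exposure window, which the section does not state.

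Several stronger readings are tempting but unsupported:

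- A reader might infer that only positive relationships are ever adjusted. The first gate is significance, so a non-significant positive endpoint is also left unadjusted.
- A reader might infer that an inverse PFS relationship is barred from adjustment. The sentence names logistic regression only.
- A reader might infer that inverse results are confounded, or that the sponsor would present one as evidence that higher exposure is harmless. The documents establish neither; they show only that such a result would be unadjusted for the listed covariates.

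**Conclusion.** The point holds as a minor defect in an exploratory analysis. For nine of the ten named endpoints, a significant inverse exposure relationship would be reported from the unadjusted model alone, by a stated rule that depends on the sign of the result. Neither document restores the adjustment.

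The size is unknown. Across the assumed settings with confounding present, a null relationship appears significantly inverse in about 8% to 99.5% of data sets, against a nominal 2.5% in one direction. No single figure in that range should be quoted as the expected error, because confounder strength, event rate and sample size are all assumptions. The conclusion about the rule rests on the text and does not need the simulation. A reader might also infer that the trial's main conclusions are exposed; they are not, since the PFS, ORR and OS tests do not use this analysis.

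**What to change.** In SAP Section 10.7.1:

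1. Delete the sentence that excludes endpoints with an inverse relationship from multiple logistic regression.
2. Apply the same covariate model to every endpoint that passes the existing significance gate, whatever its direction, and say that this includes the Cox model for PFS.
3. State that baseline covariates do not remove bias from dose holds or early stopping after an event, so an adjusted inverse safety result still needs cautious interpretation.

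There is no need to extend adjustment to non-significant endpoints. That would be a separate design change, and about ten covariates on a sparse outcome such as fatal TEAEs would risk overfitting. If the sponsor prefers to keep the exception, it should define inverse for each endpoint type and give the reason.

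The cost is a few more model fits on data already collected, in the separate exposure-response report, with limited precision for rare outcomes.
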